## Data Analysis

Demographic and other maternal characteristics will be compared between the two cohorts. The outcome analyses include:

1. comparison of proportion of PTBs among those enrolled prior to 37 weeks' gestation and resulting in a live born singleton infant between the *Boostrix*-exposed cohort and the comparison cohort by calculating hazard ratios and associated 95% confidence intervals.
2. comparison of proportion of stillbirths between the *Boostrix*-exposed cohort and the comparison cohort by calculating relative risks and associated 95% confidence intervals.
3. comparison of proportion of SGA infants ( $\leq 10^{\text{th}}$  centile for sex and gestational age) on birth weight, length, and head circumference among live born singletons between the *Boostrix*-exposed cohort and the comparison cohort by calculating relative risks and associated 95% confidence intervals.
4. comparison of proportion of preeclampsia/eclampsia diagnosed after the 1st day of the 27th week of gestation in pregnancies ending in livebirth or stillbirth between the *Boostrix*-exposed cohort and the comparison cohort by calculating relative risks and associated 95% confidence intervals.
5. comparison of proportion of cases of chorioamnionitis in pregnancies ending in livebirth or stillbirth between the *Boostrix*-exposed cohort and the comparison cohort by calculating relative risks and associated 95% confidence intervals.
6. comparison of proportion of PROM occurring after the 1st day of the 27th week of gestation in pregnancies ending in livebirth or stillbirth between the *Boostrix*-exposed cohort and the comparison cohort by calculating relative risks and associated 95% confidence intervals.
7. comparison of proportion of cases of neonatal sepsis occurring in pregnancies ending in live birth including twins or higher order multiples between the *Boostrix*-exposed cohort and the comparison cohort by calculating relative risks and associated 95% confidence intervals.

8. comparison of proportion of neonatal deaths occurring in pregnancies ending in live birth including twins or higher order multiples between the *Boostrix*-exposed cohort and the comparison cohort by calculating relative risks and associated 95% confidence intervals.

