9. comparison of proportion of NICU admissions for bronchopulmonary dysplasia occurring in pregnancies ending in live birth including twins or higher order multiples between the *Boostrix*-exposed cohort and the comparison cohort by calculating relative risks and associated 95% confidence intervals.

Initial analysis will be unadjusted. Adjusted analyses will be conducted where numbers of events permit, multivariable analyses will be conducted to adjust for possible confounders.

For the *Boostrix*-exposed cohort, follow-up time with respect to the primary and secondary outcomes will start on the date of *Boostrix* vaccination, and for the comparator cohort, follow-up time will start on the 1st day of the 27th week of gestation.

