### **Cohort 2: Tdap Vaccine-Unexposed Comparator Group**

#### Inclusion Criteria

- Currently pregnant women at the time of enrollment who were not exposed to any Tdap vaccine from the first day of LMP to the end of pregnancy.
- Currently pregnant women at the time of enrollment who agree to the conditions and requirements of the study including informed consent, the interview schedule and release of medical records.
- Availability of obstetric, delivery and pediatric medical records for the enrollment pregnancy.

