**Table 1 Exposure, Comparator and Outcome Variables**

Variable	Role	Data Source(s)	Operational Definition
Exposure to the Boostrix vaccine	Exposure	Maternal report, Vaccine record (e.g., yellow card), Medical record	Maternal report or medical record documentation of exposure to the Boostrix vaccine on or after the 1 st day of the 27 th week of pregnancy
Gestational timing of the Boostrix vaccine	Exposure	Maternal report Vaccine record (e.g., yellow card) Medical record	Maternal report or medical record documentation of the dates of the Boostrix vaccine administration on or after the 1 st day of the 27 th week of pregnancy
No Tdap vaccine exposure during pregnancy	Comparator	Maternal report Medical record	Maternal report of no exposure to any Tdap vaccine at any time from the first day of the LMP to the end of pregnancy; no documentation of Tdap vaccine in medical record
Preterm delivery	Primary Outcome	Maternal report Medical record	Maternal report and medical record documentation of a spontaneous or induced delivery after the 1 st day of the 27 th week of gestation or date of Boostrix vaccination, (whichever comes later) and <37 gestational weeks (as counted from the first day of LMP) (See Section 7.3.1 for operational definition of LMP) ( CDC, 2021 )
Stillbirth	Primary Outcome	Maternal report Medical record	Maternal report and medical record documentation of a non-deliberate fetal death that occurs after the 1 st day of the 27 th week of gestation or date of Boostrix vaccination, (whichever comes later), but prior to delivery ( Prager, 2021 )
Small for gestational age infant	Primary Outcome	Maternal report Medical record	Maternal report and medical record documentation of birth size for liveborn infants born after the 1 st day of the 27 th week of gestation or date of Boostrix vaccine, whichever comes later) (weight, length, or head circumference) $\leq 10^{\text{th}}$ percentile for sex and gestational age using NCHS pediatric growth curves for full term infants. Prenatal growth curves specific to preterm infants are used for preterm infants ( Olsen, 2010 ; Schlaudecker, 2017 )

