Preeclampsia / eclampsia	Secondary Outcome	Maternal report Medical record	Maternal report and medical record documentation of preeclampsia. Preeclampsia is defined as hypertension in conjunction with at least one of the following: proteinuria; thrombocytopenia; impaired liver function; renal insufficiency; pulmonary edema; or visual or cerebral disturbances. The disorder usually occurs after 20 weeks of pregnancy and worsens over time.

Variable	Role	Data Source(s)	Operational Definition
			Eclampsia is a life-threatening condition that is considered a complication of severe preeclampsia and characterized by coma and/or seizures that are unrelated to a preexisting brain condition. Onset of preeclampsia/eclampsia as an outcome for this study is defined as onset after the 1 st day of the 27 th week of gestation or Boostrix vaccination date (whichever comes later).
Premature rupture of the membranes (PROM)	Secondary Outcome	Maternal report Medical record	Maternal report and medical record documentation of premature rupture of the membranes (amniotic sac). Premature rupture of the membranes is before labor begins on or after the 1 st day of the 27 th week of gestation or date of Boostrix vaccination (whichever comes later) and prior to 37 weeks' gestation.
Chorioamnionitis	Secondary Outcome	Maternal report Medical record	Maternal report and medical record documentation of chorioamnionitis. Chorioamnionitis classified using Brighton collaboration definition ( Kachikis, 2019 ) Please refer to details in Appendix 1
Neonatal sepsis of early onset	Secondary Outcome	Maternal report Medical record	Maternal report and medical record documentation of neonatal sepsis. Sepsis defined as isolation of pathogenic species from blood or cerebrospinal fluid culture within 72 hours of birth and antibiotic treatment for at least 5 days or until death (provisional definition pending confirmation of the ability to implement extraction in medical records)
Neonatal intensive care (NICU) for bronchopulmonary dysplasia	Secondary Outcome	Maternal report Medical record	Maternal report and medical record documentation of NICU care for bronchopulmonary dysplasia. Admission to the NICU defined as admission for any number of days for diagnosis of bronchopulmonary dysplasia

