The primary analyses will be performed to estimate the causal relative risk using the method of inverse probability weighting (IPW) based on the PS. In the IPW approach, we will use stabilized weights that are further trimmed to be between 0.1 and 10 if necessary (Austin, 2015). The 95% CIs will be obtained using the bootstrap estimated variance and asymptotic normality, with 200 bootstrap samples.

A secondary analysis will be conducted using outcome regression, i.e., a logistic regression model will be fitted with the binary outcome (Y), and exposure (A) and propensity score (L) as regressors. Standardization will be performed to obtain the

estimated causal risk ratio (Hernán, 2019), which has the interpretation as the marginal or population averaged risk ratio. The CIs are obtained by bootstraps.

For the endpoint of **preterm delivery**, only pregnancies ending in delivery after the 1st day of the 27th week of gestation or the date of *Boostrix* vaccination (whichever comes later), enrolled prior to 37 weeks' gestation, and whose pregnancies result in a live-born singleton will be included in the analysis. Further, in the *Boostrix*-exposed group, exposure to vaccine must take place between the 1st day of the 27th week of gestation and before 36 weeks' and 5 days (allowing at least one day after vaccination for preterm delivery). Because women can meet criteria for eligibility for the study at arbitrary times following the 1st day of the 27th week of gestation, they may not be followed from the beginning of the relevant gestational age window. Those who experience the event prior to enrollment will never enter the study, leading to left truncation of the time to event. This can produce selection bias. In addition, vaccine exposure can occur on or any time after the 1st day of the 27th week of gestation in pregnancy, so exposure status is time-dependent. To address these issues, survival analysis methods will be used. Fleming-Harrington estimate at 37.0 weeks' gestation will be used to estimate the preterm delivery rate and 95% CI in each of the cohorts (Fleming, 1984; Pan, 1998). The Cox proportional hazards marginal structural model (MSM) incorporating time-dependent vaccine exposure and relevant covariates will be used to estimate the causal hazard ratio (HR) and 95% CI (Hernán, 2001).

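### Stillbirth is compared as a ratio of proportions, with follow-up from vaccination in one cohort and from week 27 in the other, so immortal time pulls the relative risk below 1

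*Protocol*

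**What the plan says.** **Start of follow-up.** The last paragraph of Data Analysis in the protocol's abstract (section 2) states that for the exposed cohort "follow-up time with respect to the primary and secondary outcomes will start on the date of" Boostrix vaccination, whereas "for the comparator cohort, follow-up time will start on the" first day of week 27.

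**Comparator.** Section 7.2.1, Cohort 2, admits women "who were not exposed to any Tdap vaccine from the first day of LMP to the end of pregnancy". Membership is therefore known only once the pregnancy is over.

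**Event window.** Table 1 counts a stillbirth only after week 27 begins or after vaccination, whichever is later. For comparators this is always week 27, so only the exposed window is shortened.

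**Effect measure.** Item 2 of the abstract's list is a "comparison of proportion of stillbirths between the" two cohorts, as a relative risk with a 95% confidence interval. SGA and all six secondary outcomes also get relative risks. Only preterm birth gets a hazard ratio.

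**Recognition.** For preterm delivery, section 7.7.1 explains that late entry truncates the data and that vaccination can come at any time in the window, "so exposure status is time-dependent. To address these issues, survival analysis methods will be used". A Cox marginal structural model with time-dependent exposure follows. Nothing similar is stated for stillbirth.

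**Preeclampsia and PROM.** Abstract items 4 and 6 count events after the first day of week 27 in both cohorts. Table 1 is narrower: "Onset of preeclampsia/eclampsia as an outcome for this study is defined as onset after the" later of that day and vaccination for preeclampsia, with a similar rule for PROM.

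**The concern.** A vaccinated woman must still be pregnant with a live fetus on her vaccination date, and nothing before that date can count against the vaccine. A woman who meant to be vaccinated at 31 weeks and has a stillbirth at 29 weeks is, by definition, never vaccinated: she adds a case to the comparator. The exposed cohort thus has guaranteed event-free weeks, and the comparator also receives the early events of women who intended vaccination.

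In a safety study this error points toward no harm. Propensity weighting balances covariates but does not move time zero. The sensitivity analyses in section 7.7.2 and the limitations in section 7.9 do not mention the issue. It cannot simply be left to the SAP either: the start rule, comparator definition, event window and effect measure are all fixed in the protocol.

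**Working it through.** The protocol gives no stillbirth figure to reproduce; Table 4 omits stillbirth, and section 7.5 says only that high relative risks will be detectable. The check asks what relative risk the rules produce when the vaccine does nothing.

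**Inputs**
- From the protocol: uptake u = 55%, preterm birth 10%, preferred vaccination window 27–36 weeks.
- Assumed: vaccination spread evenly over 27–30, 27–32 or 27–36 weeks, so mean delay m = 1.5, 2.5 or 4.5 weeks; constant weekly stillbirth hazard h (about 0.5% in total after week 27); term births at a mean of 39.3 weeks; preterm births a mean of 6.67 weeks after week 27.

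**Hand calculation, all women enrolled before week 27**
- Mean time at risk: T = 0.9 × 12.3 + 0.1 × 6.67 = 11.74 weeks.
- Exposed risk ≈ h(T − m).
- Comparator risk ≈ hT + hm·u/(1 − u); the second term is the early stillbirths of women who intended vaccination. Here u/(1 − u) = 0.55/0.45 = 1.222.
- Null RR ≈ (T − m)/(T + 1.222m). The hazard cancels.
- m = 1.5: 10.24/13.57 = 0.75. m = 2.5: 9.24/14.80 = 0.62. m = 4.5: 7.24/17.24 = 0.42.

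**Simulation**, 4 million pregnancies per scenario, no vaccine effect, 55% uptake:

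| Analysis | 27–30 wk | 27–32 wk | 27–36 wk |
|---|---|---|---|
| Stillbirth RR by the protocol's rules, early enrollment | 0.77 | 0.65 | 0.45 |
| Rates from each cohort's own start, never-vaccinated comparators | 0.87 | 0.81 | 0.69 |
| NICU for bronchopulmonary dysplasia, assumed only in births before 32 weeks | 0.76 | 0.49 | 0.23 |
| Preeclampsia, Table 1 window | 0.98 | 0.96 | 0.85 |
| Chorioamnionitis, assumed threefold risk in preterm births | 0.99 | 0.98 | 0.91 |
| SGA unrelated to gestational age | 1.00 | 1.00 | 1.00 |

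The simulated stillbirth values lie slightly above the hand values because women who deliver live before a planned vaccination also join the comparator, as non-cases. Over 40–70% uptake the stillbirth RR ranged from 0.36 to 0.80. Counting pre-vaccination weeks as unexposed time returned 0.98 to 1.03, so the time handling causes the shift.

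**Enrollment timing.** Participants may enroll at any point in pregnancy, and a late enrollee is event-free up to that point in either cohort. With enrollment spread over 26–38 weeks, the null stillbirth RR was 0.96/0.91/0.71 in one simulation and 0.92/0.86/0.61 in another that started the window at 26 weeks. With that earlier start, early enrollment gave 0.65/0.54/0.40.

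**Preeclampsia under the abstract's window.** Counting diagnoses after week 27 in both cohorts gave null RRs of 1.00 to 1.07, which is not protective.

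**What a bias of this size hides.** With a factor of 0.65, a true stillbirth RR of 1.5 would appear as 1.5 × 0.65 = 0.98.

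**The case against.** A reader might infer that every outcome except preterm birth is made to look protective. The documents do not support that. SGA is essentially unaffected unless it is linked to early delivery. Chorioamnionitis moves little. For preeclampsia and PROM the protocol gives two windows, and the protective direction for preeclampsia appears only under Table 1.

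A reader might also infer that preterm delivery is biased because the abstract's start rule discards the unexposed weeks of later-vaccinated women. The abstract does not say that those weeks are dropped. Section 7.7.1 specifies time-dependent exposure and an estimator for truncated data, which covers both the weeks before vaccination and delayed entry. The two passages need one reconciling sentence; preterm delivery has no established bias.

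It is also fair to say that the comparisons are not purely crude: section 7.7.1 plans propensity-weighted relative risks for SGA and chorioamnionitis, and adjusted analyses elsewhere where numbers permit. That stands as description, but weighting does not realign the start of follow-up.

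The strongest objection concerns size. The protocol gives no distribution of vaccination or enrollment timing, and late enrollment shrinks the bias considerably. Birth before 32 weeks is also no stand-in for neonatal death, which Table 1 does not restrict by gestational age. Finally, at an assumed 0.5% there would be about 1,500 × 0.005 = 7.5 stillbirths per cohort, so an elaborate weighted model would be unstable. All of this stands; none of it changes the direction for stillbirth.

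**Conclusion.** The point holds for stillbirth. The protocol's rules build in immortal time and pull the null relative risk below 1 in every scenario tried: illustratively 0.45–0.77 with early enrollment (lower still if the window opens at 26 weeks) and about 0.6–0.96 with late enrollment. These sizes rest on assumed vaccination timing, enrollment timing and a constant hazard; the direction follows from the definitions.

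NICU admission for bronchopulmonary dysplasia is biased the same way, as is neonatal death to the extent that it follows early birth. The effect is small for chorioamnionitis and near nil for SGA unless it is linked to early delivery. For preeclampsia and PROM it cannot be settled until the two windows are reconciled. Because stillbirth is a primary safety outcome and the error favours a finding of no harm, the rule should be changed before analysis.

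**What to change.** 1. Replace the abstract's start rule: every woman enters at the later of enrollment and the first day of week 27, with vaccination as a time-dependent exposure. This brings it into line with section 7.7.1.
2. Analyse stillbirth this way with a simple time-dependent Cox or rate-ratio model, given the few events. Alternatively, compare each vaccinated woman with women enrolled, still pregnant and unvaccinated on the same gestational day. Use that matched index day for the neonatal outcomes.
3. Let registry women who later receive another Tdap brand contribute unexposed time, or serve as comparators, until that vaccination, and censor them there. They now belong to neither cohort. If half of vaccinees receive another brand (assumed), a time-dependent analysis of the two existing cohorts alone still gives null rate ratios of 0.92/0.91/0.84 for the three vaccination spreads; a second set of assumptions gave 0.90/0.86/0.83. Adding these women restored about 1.0.
4. Reconcile the preeclampsia and PROM windows between the abstract and Table 1, and exclude women with the event before entry where onset dates can be abstracted.

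**Cost.** Vaccination dates, gestational age at enrollment and delivery or stillbirth dates are already captured, so much of this is programming. The change also needs the records of women given another Tdap brand. Onset dates for preeclampsia and PROM must be abstracted, because section 7.4.1 lists only a description of these complications. Stillbirth would be reported as a hazard or rate ratio with wide intervals.

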### **Milestones**

Planned dates of study milestones:

- Start date of data collection: 01 March 2023
- Last date of data collection: 31 December 2027
- Annual progress report submission: Annually beginning December 2023 through December 2027
- Final study report submission: 31 August 2028

### **3. AMENDMENTS AND UPDATES**

Not applicable.

## 4. MILESTONES

Milestone	Planned date
Start of data collection	01 March 2023 
End of data collection	31 December 2027 
Study enrollment report	Monthly until end of recruitment
Annual status report of Postmarketing Requirements/Commitments due By:	06 December 2023 06 December 2024 06 December 2025 06 December 2026 06 December 2027
Registration in the European Union post-authorization studies (EU PAS) register	To be confirmed
Final study report submission	31 August 2028

 Pregnant women participating in the OTIS/MotherToBaby Pregnancy Registry on or after 08 March 2004 are eligible for study inclusion; however, selection of the 600 eligible pregnancies in each cohort from those enrolled prior to 01 March 2023 will be prioritized to include most recent years of enrollment. The start of data collection is defined as the planned date for starting data review for the first annual progress report.

 The end of data collection is defined as the planned date on which the analytic dataset will be first completely available; the analytic dataset is the minimum set of data required to perform the statistical analysis for the study objectives.

## 5. RATIONALE AND BACKGROUND

### 5.1. Background

A US *Boostrix* pharmacovigilance pregnancy registry was initiated in 2005 ([Kuznetsova, 2022](#)) when *Boostrix* was licensed in the United States (US) for active booster immunization against diphtheria, tetanus, and pertussis (Tdap) in individuals aged 10 years and older. In June 2011, the US Advisory Committee on Immunization Practices (ACIP) recommended immunization of pregnant women against pertussis as a mean to protect their infants, who are vulnerable until they can receive their primary vaccination. ([CDC, 2013](#)). In October 2012, ACIP recommended that the Tdap vaccine be given to women during every pregnancy (preferably between 27–36 weeks gestation). Since 2014 the maternal Tdap uptake measured by surveys conducted by the US Centers for Disease Control (CDC) has plateaued at 55% ([Baïssas, 2021](#)). Two Tdap vaccine brands are used for immunization during pregnancy in the US ([CDC, 2017](#)).

The previous *Boostrix* US pregnancy registry EPI-PERTUSSIS-028 VS US PR (201327) was aimed at assessing the proportion with any abnormal pregnancy outcomes among registered pregnancies (women vaccinated with *Boostrix* during pregnancy or within 28 days preceding conception). From May 2005 to August 2019, 1,517 (1,455 prospective

and 62 retrospective) pregnancy reports were received from the pregnancy registry (Kuznetsova, 2022). Of the prospective reports, there were 1,188 lost to follow-up and 250 had known outcomes: 244 live infants with no apparent birth defects, 3 live infants with birth defects, and 3 spontaneous abortions with no apparent birth defects. Data from the *Boostrix* US pregnancy registry EPI-PERTUSSIS-028 VS US PR (201327) raised no safety concerns regarding *Boostrix* maternal immunization (Kuznetsova, 2022). However, the findings from the registry were limited by the modest number of follow-up reports (N=250) and the lack of representativeness of all pregnancies, the high proportion of loss to follow-up and the absence of a comparison cohort who were unexposed to Tdap vaccination during pregnancy.

On October 7 2022, the US Food and Drug Administration approved *Boostrix* for immunization during the third trimester of pregnancy to prevent pertussis in infants younger than two months of age (US FDA, 2022). This revised registry aims at monitoring the safety of *Boostrix* in this indication and is a postmarketing commitment.

To date, no specific safety concerns have been identified for Tdap maternal immunization (Vygen-Bonnet, 2020; Hall, 2020; Mohammed, 2021; Fakhraei, 2021), including *Boostrix*-specific studies (Perrett, 2020a; Perrett, 2020b; Petousis-Harris, 2019; Sancovski, 2019; Tseng, 2022).

The *Boostrix*-specific studies also include a large observational study (NCT03463577) conducted in the US by Kaiser Permanente Southern California (KPSC) in which the safety of *Boostrix* was assessed in 16,606 pregnant individuals who received *Boostrix* on or after the 27th week of pregnancy in 2018–19 compared with a historical cohort of individuals who were pregnant in 2012–14 and did not receive any Tdap vaccine during their pregnancy (Tseng, 2022). The study assessed a wide range of fetomaternal and neonatal outcomes. Overall, the study results support the safety of *Boostrix*.

For *Boostrix* specifically, the study conducted at KPSC found an elevated adjusted relative risk (aRR) for intra-uterine infection (aRR = 1.28, 98.75% confidence interval [CI]: 1.12–1.47) within the pre-determined significance levels (the upper limit of the 98.75% CI for the aRR was below 2) and this increase was consistent with the background increasing trend of this diagnosis among all pregnant individuals at KPSC since 2011 (before the study vaccination period). This may reflect improved obstetric care. The other *Boostrix*-specific studies, including a clinical trial in pregnant subjects (Perrett, 2020a) and a population-based observational study in New Zealand (Griffin, 2018), did not find evidence of an increased risk.

The new registry study is intended to add to the existing safety data for *Boostrix* as compared to the US pregnancy registry EPI-PERTUSSIS-028 VS US PR (201327) and will be established in collaboration with the OTIS/MotherToBaby Research Center, an organization with well-established measures proven to efficiently retain participants and provide more complete and meaningful data.

